## **5.0 Selection of Subjects**

## **5.1 Study Population**

The study population includes frail veterans scheduled to undergo high-risk surgical procedures. Veterans scheduled for surgery are evaluated in either the Pre-Anesthesia Evaluation Clinic (PAEC) or the Preoperative Optimization of Senior Health (POSH) Clinic. We plan to screen veterans who are seen in either clinic and enroll a total of 24 patients over 2 years.

## **5.2 Inclusion and Exclusion Criteria**

### **5.2.1 Inclusion Criteria**

- Scheduled for high-risk surgery (colorectal, major urologic, hepatobiliary, esophageal, thoracic).
- Time from assessment to surgery  $\geq 21$  days
- Age  $\geq 50$  years
- English speaking
- 5RSTS time  $\geq 11$  sec and/or TMST score  $\leq 25\%$  percentile for gender/age

### **5.2.2 Exclusion Criteria**

- Montreal Cognitive Assessment (MoCA) score of  $<21$  (high school education) or 20 ( $<$  high school education) or Saint Louis University Mental Status (SLUMS) score  $\leq 20$
- Dementia diagnosis documented in electronic health record
- Inability to complete physical function assessment
- ASA PS categories 4 or 5
- Currently residing in skilled nursing facility
- Lack of access to a telephone
- Advanced chronic kidney disease (KDIGO stage 4 and 5)
- Pregnant at the time of preoperative assessment
- Inability to receive SMS text messages (i.e. does not own a text-enabled cellular telephone or tablet)

## **5.3 Inclusion of Women and Minorities**

It is the policy of our institution (Durham VAHCS) not to discriminate against any patient because of sex, age, ethnicity, race, sexual orientation, or any other attribute. Therefore, all patients, including those who are lactating or otherwise of childbearing potential (excluding those who are pregnant), who present for surgery at DVHCS and meet inclusion/exclusion criteria would be eligible for inclusion in this study. Given that the small size of the cohort, and the focus of this study (feasibility, acceptability, safety, and effect size estimation), we do not plan to analyze racial, ethnic or gender groups separately.

## **6.0 Subject Recruitment**

For the purposes of screening, recruiting, and determining eligibility, information will be obtained by accessing medical records—a HIPAA Waiver to screen and recruit will be requested. Once eligibility is determined, patients will be approached for interest and enrollment during their preoperative visit, typically 3-4 weeks prior to surgery. At that time, they will have adequate time to consider the study and its benefits and risks, ask questions, and decide if they wish to take part. Written informed consent will be obtained by study personnel.

## **7.0 Consent Process**

### **7.1 Screening**

Patients will be identified in 3 ways:

- (a) Information about this new prehabilitation pilot program will be disseminated among our surgical colleagues. Surgeons will be encouraged to alert the PREVENT team to any patients being evaluated in the Surgery clinic who may be good prehabilitation candidates (frail, undergoing high-risk surgery).
- (b) Additionally, a list of proposed cases is currently available in our Perioperative Scheduling Software (DSS) and in the VA's Corporate Data warehouse (CDW). This list will be screened periodically to identify potential candidates.
- (c) Finally, the list of patients scheduled for evaluation in the PAEC and POSH clinics will be reviewed for potential prehabilitation candidates (review of Anesthesiology E-Consult or POSH Consult requests).

A HIPAA Waiver for screening purposes will be requested so that eligible participants can be identified prior to their PAEC or POSH clinic appointment, if possible ~4 weeks or more before their proposed operation.

### **7.2 Eligible Patients**

When an eligible patient is identified, the day of the PAEC/POSH appointment will be determined. On the day of the clinic visit, the MoCA or SLUMS score, and physical function assessments (routinely performed by nursing staff during the clinic visit) will be reviewed to establish final eligibility for inclusion in the study, and the research coordinator or an investigator will be notified. A study coordinator or investigator will review the ICF with each eligible patient, answering all questions or concerns. After a review of the ICF, the patient will sign under the supervision of the study personnel and a full copy provided to the patient and/or family member. Study personnel may discuss the project with their other physicians or family members as needed.

All study personnel have completed the VA Human Subjects Protections and Good Clinical Practices training requirement and have experience with the process of obtaining and documenting informed consent for research. Any new study personnel who have not had such experience will be trained in several stages, including verbal instruction, shadowing consenting visits, VA training modules, and observation by qualified personnel.

No study procedures will be performed until after the ICF and HIPAA Authorization have been signed and received. Patients with impaired decision-making capability will

not be included in this study. Original signed copies of the informed consent form and HIPAA Authorization will be kept in our research office (C3011A) while photocopies will be provided to patients for their use.

## 8.0 Study Interventions

[figure not shown]
### 8.1 Screening Procedures

Patient screening will begin with a review of the proposed surgical cases list in DSS and CDW, review of Anesthesiology e-consults (PAEC or POSH) and direct surgical referrals (as described above in Section 7.1, Screening). A review of the patient's medical record via CPRS on the day of the PAEC/POSH clinic visit will verify that they meet inclusion/exclusion criteria.

Patients meeting all inclusion criteria by chart review will then undergo a baseline physical function assessment at the time of their PAEC or POSH in-person visit using the TMST and 5RSTS tests (as above, part of standard clinic evaluation). Eligible patients who consent to participate will then complete a baseline assessment that includes anthropometrics, assessment of handgrip strength (HGS), and the PG-GSA, SF-36 and HADS questionnaires.

### 8.2 Study Procedures

Eligible veterans who consent will enroll in a program of individualized exercise training combined with nutritional support during intervening time before and after surgery.

Study procedures and assessments are outlined in Figure 1 below.

#### **Figure 1. Study milestones and assessments**

Subjects who do not have a smart phone or tablet or who prefer not to use their own devices will receive a *VA-issued tablet* device that they will use to interact with their exercise trainer. They will be asked to download the Annie texting app and a teleconference platform app on either their personal device or the VA-issued device. The VA issued tablets are then the property of the participant and no VA data will be stored on them. Automated text messaging via the VA Annie App will supplement our patients' exercise and nutritional support efforts.

#### **8.2.1 Exercise Program**

The exercise program will consist of a progressive function-based exercise program that includes 3 days per week of supervised exercise delivered directly to the home using telehealth technology. Exercise prescriptions will be individualized to baseline fitness and functional capacity.

Supervised exercise will consist of progressive, rotating, low-impact training interspersed with brief rest periods aimed at progressing to 30-minutes of moderate intensity aerobic training. Intensity of effort will be titrated to rate-of-perceived-exertion (RPE), with a target of 4-6 out of a maximum of 10 per national guidelines for older adults. Resistance and functional training will be included and focus on strengthening the large muscle groups of the core, upper and lower extremities, and on maximizing mobility using body weight or resistance bands when the participant reaches higher levels of RPE (6-7).

Activities will be constantly monitored and adjusted to increase difficulty but stay below the target ceiling of 6-7 RPE. Due to the limited time window, each participant will be challenged daily to increase some element of the exercise program. A detailed description of the proposed exercise routine is included in Appendix 2. Post-operative aerobic and strength exercise will follow similar progression beginning as early as 1 week postoperatively. Exercise staff will work closely with surgical staff to safely provide exercise progressions given some surgeries may contraindicate specific exercises and intensities.

#### **8.2.2 Nutritional Support Program**

The nutrition intervention will be directed by a Registered Dietitian Nutritionist and will consist of tailored nutritional advice at the time of enrollment, followed by high quality protein supplementation individualized for kidney function (1.5 gm/kg/day for patients with normal kidney function, 1.2 gm/kg per day for patients with KDIGO GFR categories G3a and G3b). Patients with KDIGO GFR category G4 or G5 will be excluded (see Appendix 3). These recommendations are in accordance with current clinical guidelines for nutrition in the perioperative period.

Multivitamin and vitamin D supplementation will be provided (50% of RDA) during prehabilitation and recovery. Preoperatively, a 3-4-week supply of supplements will be provided at the PAEC or POSH clinic visits (T1). At the time of hospital discharge, participants will be given an additional six-week supply.

### **8.2.3 Assessments and Supplemental Interventions**

Objective physical function assessments will be performed at baseline (T1), before surgery (T2), immediately prior to hospital discharge (T3), and then again 6 weeks postoperatively (T4) by administering the **2MST,5RSTS and HGS tests** either in-person or remotely using telehealth technology (see Table 1 for details).

The nutritional support intervention will be assessed at baseline (T1), before surgery (T2), immediately prior to hospital discharge (T3) and then again 6 weeks postoperatively (T4) using **anthropometrics**, a weekly **24-hour dietary recall** (via telephone or videoconference, see Appendix 6), and the administration of the **PG-GSA**, a validated nutritional assessment instrument (see Table 1 for details).

Both the exercise and nutritional support programs will be supplemented with **text messages** on veterans who own text message-enabled cellphones.

Messages will be sent daily using the VA Annie App during the prehabilitation period (T1 - T2). The purpose of these messages is as a reminder about the timing of training sessions, to prompt independent exercise on days between formal sessions, to take protein supplement following exercise, and to maintain a nutritional diary (see above).

Text messages and weekly telephone or videoconference calls will resume upon hospital discharge and extend until the 6-week follow-up visit (T4).

Anxiety, depression, and health-related quality of life will be assessed using the HADS and SF-36 questionnaires at baseline (T1), before surgery (T2), immediately prior to hospital discharge (T3), and 6 and 24 weeks postoperatively (T4 and T5, respectively). These questionnaires will be administered either in person or via telephone or videoconference.

Details and timelines for each of these assessment instruments are described in Table 1.

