**Table 1. Assessments of physical function & mobility, nutrition, anxiety/depression, and health-related quality of life**

Domain	Measure	Details	When Collected
Screening Measures			
Medical History		A chart review will be conducted for every potential participant to assess eligibility (see criteria above) and to document surgery type.	Baseline (T1)

 The HGS test will only be administered when the assessment is conducted in person

Cognition		Participants must have a score of $\geq 20$ (< high school education) or $\geq 21$ (high school or more) on the MoCA or a score of $\geq 21$ on the SLUMS test and able to do ADLs to qualify for participation in this study. 	T1
Outcome Measures			
Demographics		Standard demographic information will be gathered via self-report and physical examination at baseline to describe the study sample.	T1
Physical Function & Mobility	5RSTS	The five repetition sit-to-stand test (5RSTS) is widely used as an indicator of lower limb strength among older adults.  The test is easy to administer and has good to high test-retest reliability.  In a meta-analysis conducted to generate normative values for this test, patients older than 60 years of age exceeding 11.4 sec were considered to have worse than average performance. 	T1, T2, T3, T4
	TMST	The two-minute step test (TMST) requires that individuals march in place as fast as possible for 2 minutes while lifting the knees to a height midway between their patella and iliac crest when standing. The performance on the test is defined as the number of right-side steps of the criterion height completed in 2 minutes. 	T1, T2, T3, T4
	HGS	Handgrip strength can be quantified by measuring the amount of static force that the hand can squeeze around a dynamometer. Low handgrip strength is a clinical marker of poor mobility and a better predictor of clinical outcomes than low muscle mass. Grip strength may also be used as a reliable surrogate for more complicated measures of muscle strength in the lower arms or legs.	T1, T2, T3, T4
Nutrition	Anthropometrics	Anthropometric measurements, including body mass index (BMI, weight in kilograms over the square of height in meters), mid-upper arm circumference, upper thigh circumference, waist circumference, hip circumference, and waist-to-hip ratio.	T1, T2, T3, T4

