## 10.0 Costs and/or Payments to Subjects

Participants will be reimbursed \$50 for each in-person clinic visit they make for purposes of study procedures (range \$100-\$200). The initial preoperative visit and the 6-week postoperative visit for all participants with an optional second preop visit immediately prior to surgery if the T2 assessment cannot be performed on the day of surgery and at T5 if the assessments cannot be performed over the telephone.

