## **13.0 Data Analysis and Statistical Considerations**

Feasibility will be assessed by calculating the acceptance rate, measured as the number of patients enrolled divided by the number eligible. In addition, we will evaluate veterans' reasons for enrollment or non-enrollment in the program using patient interviews and semi-structured questionnaire (see Appendix 4). No PHI will be recorded in questionnaires obtained from eligible but non-recruited veterans.

Acceptability will be measured by rate of compliance with the exercise/nutrition programs. For the exercise intervention, the percentage of patients completing  $\geq 75\%$  of sessions divided by the number of enrolled patients will be calculated. For the nutritional intervention, compliance will be measured by the percentage of patients with  $\geq 75\%$  adherence to protein intake goal, as assessed using the text message-based nutrition diary, lids returned, and 24-hour recall administered during the weekly telephone call.

Safety will be evaluated by the number of adverse events (significant injury or medical event) during exercise. A significant injury or medical event is defined as an event that causes the participant to seek attention from a health professional or limits their activities of daily living for at least two days.

Effect size will be estimated by comparing physical function before and after the prehabilitation intervention, as measured by the 5RSTS and the 2-minute step tests using Cohen's D. Changes in health-related quality of life (SF-36) and anxiety and depression (HADS) before surgery and at the 6-week and 24-week study periods following surgery will be calculated.

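### The step test and sit-to-stand test may be remote at T2 although T1 is in person, and the before-after effect size neither records nor accounts for the change of mode

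*Combined protocol and SAP*

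**What the plan says.** **Baseline mode.** Section 8.1 describes a "baseline physical function assessment at the time of their PAEC or POSH in-person visit using the TMST and 5RSTS tests". Section 7.2 adds that nursing staff routinely perform these assessments at that visit. T1 is therefore in person.

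**Later mode.** Section 8.2.3 schedules the step test, the five-repetition sit-to-stand (5RSTS) and handgrip strength at T1, T2 (before surgery), T3 (before discharge) and T4 (6 weeks), to be done "either in-person or remotely using telehealth technology". It refers to Table 1 for details. Table 1 gives time points and test descriptions but no rule on mode. A footnote shows that remote testing is really expected: "The HGS test will only be administered when the assessment is conducted in person".

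**Visits provided for.** Section 10.0 pays $50 "for each in-person clinic visit they make for purposes of study procedures", with a stated range of $100–$200. It lists "The initial preoperative visit and the 6-week postoperative visit for all participants", an "optional second preop visit immediately prior to surgery if the T2 assessment cannot be performed on the day of surgery", and a visit "at T5 if the assessments cannot be performed over the telephone".

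**Analysis.** Section 13.0 states: "Effect size will be estimated by comparing physical function before and after the prehabilitation intervention". The measures are 5RSTS and the step test, and the statistic is Cohen's d. Mode is not mentioned. Section 3.0 expects a d of about 1.6 for functional capacity, and 24 patients are planned.

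**The concern.** A before-after difference is clean only if the measurement is made the same way both times. Here the first measurement is made in a clinic and the second may be made at home over a video link.

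There are two reasons to think mode could matter. First, the step test counts only steps that reach a criterion knee height (Table 1), so an assessor has to judge each step, and that judgement may differ over video. Second, the supervised training is itself delivered to the home by telehealth, three days a week, and includes marching and chair stands (Section 8.2.1 and Appendix 2). A remote T2 would repeat practised movements in the training setting, which could flatter the result.

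With one cohort and no control arm, a mode shift does not cancel, and more patients would not remove it. Remote testing is also unlikely to fall at random, because the program is aimed partly at rural veterans and those without transport (Section 2.0). The resulting d is meant to inform a larger trial, so a distorted value would carry into that trial's planning. A secondary consequence is that handgrip strength is missing at every remote visit.

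**Working it through.** **1. Reproduce the plan's own figure.** The documents contain no power calculation. The one figure that bears on mode is the payment range in Section 10.0.

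- T1 and T4 for everyone: 2 × $50 = $100, the lower limit.
- Adding the optional T2 and T5 visits: 4 × $50 = $200, the upper limit.

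The range reproduces exactly. Section 10.0 thus counts T4 as in person for all and has a paid route to an in-person T2. T5 carries no function test.

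**2. Find where mode can change.** T1 is in person and T3 falls just before hospital discharge. A change of mode therefore arises mainly at T2 and T4. The only function d in Section 13.0 compares before with after prehabilitation, that is, T1 with T2. T2 mode is what matters for it.

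**3. Size the bias.** Let *f* be the share of T2 tests done remotely and *m* the remote-minus-in-person shift, in SDs of the change. Section 13.0 does not name the standardizer for d, so the SD of the change is an assumption, as are *f* and *m*.

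- Bias before allowing for extra spread: *f* × *m*.
- Apparent d: (d ± *f m*) / √(1 + *f*(1 − *f*) *m*²).

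| *f* | *m* | *f* × *m* | True d 1.6 reads as |
|---|---|---|---|
| 0.25 | 0.2 | 0.05 | 1.54 or 1.64 |
| 0.25 | 0.5 | 0.125 | 1.44 or 1.69 |
| 0.50 | 0.5 | 0.25 | 1.31 or 1.80 |
| 0.75 | 0.5 | 0.375 | 1.20 or 1.93 |

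The last row in full: √(1 + 0.75 × 0.25 × 0.25) = 1.023; (1.6 − 0.375)/1.023 = 1.20; (1.6 + 0.375)/1.023 = 1.93.

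**4. The case where Section 10.0 is followed.** Suppose only 2 of 24 T2 tests are remote (assumed). With *m* = 0.5 the bias is 2/24 × 0.5 = 0.04, which is negligible.

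**5. Compare with sampling error.** The 95% confidence interval for a paired d of 1.6 at n = 24, by the noncentral t, is 0.98 to 2.20. All the apparent values in the table lie inside it.

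**6. Cost of analyzing same-mode pairs only.** With T1 in person, dropping remote T2 tests leaves 24 × 0.75 = 18 patients at *f* = 0.25, or 24 × 0.25 = 6 at *f* = 0.75. For d = 1.6 the interval becomes 0.88 to 2.30, or 0.32 to 2.82.

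**The case against.** The strongest reply is that the plan largely handles this already. T1 is in person, T4 is listed as a visit for all, and T2 is expected on the day of surgery or at a paid extra visit. On that reading remote testing is a fallback and few pairs are discordant. Figure 1 is not shown in the text available and may state the mode. This is a 24-patient feasibility pilot, and even the worst assumed bias is 0.375/1.6 = 23% of the expected d and lies within sampling error. These points stand and limit the size of the concern. They do not close the gap: Section 8.2.3 as written permits either mode, the T2 visit is optional, and nothing records which mode was used.

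Three stronger readings are tempting and are not supported:

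- **That the effect size is biased.** The documents show no mode shift and give no direction. They also do not describe how knee height, chair or timing would be handled remotely. A bias is possible, not demonstrated.
- **That the bias could equal the expected effect.** The 0.4 in Section 3.0 is for quality of life, which this issue does not touch. The relevant figure is 1.6.
- **That a remote T4 distorts the stated result.** Section 13.0 writes out no T4 function analysis. T4 mode bears only on the postoperative function data collected under the second aim. Handgrip strength is likewise outside the Section 13.0 analysis, and its loss at remote visits is disclosed.

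A reader might also conclude that the main d should be confined to same-mode pairs. That would drop the patients who are remote for reasons such as distance or frailty, bringing a selection bias of its own and, as step 6 shows, much wider intervals.

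**Conclusion.** The concern holds in a limited form. Sections 8.1, 8.2.3 and 13.0 together allow an in-person T1 to be compared with a remote T2 in an uncontrolled d, with mode neither recorded nor analyzed. Under assumed remote shares of 25–75% and shifts of 0.2–0.5 SD of the change, the bias would be about 0.05–0.38 in either direction against an expected d of 1.6. It would be small if T2 is run as Section 10.0 provides. Both assumed quantities are illustrative. The case for acting is that the exposure is avoidable at little cost, not that a material error has been shown.

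**What to change.** - **Section 8.2.3:** bring it into line with Section 10.0. Make in-person testing the default for the T2 function tests (day of surgery, or the optional paid visit) and for T4 (the 6-week visit listed for all). Allow remote testing only as a fallback, so that patients who cannot travel still contribute data.
- **Data collection:** record the mode at every function assessment.
- **Section 13.0:** keep all T1–T2 pairs in the main d, and add a sensitivity analysis restricted to same-mode pairs. Report the number of pairs in each.

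The cost is a few sentences, one data field and one extra analysis. Some patients would make the optional preoperative visit, which the stated $100–$200 range already covers: T1, T2 and T4 come to 3 × $50 = $150. The sample size stays at 24.

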### **3.0 Design**

The objective of this protocol is to determine the feasibility, acceptability, and safety and estimate the effect size of a multimodal prehabilitation program that incorporates exercise training and nutritional support. The central hypothesis is that a short-duration, individualized multimodal prehabilitation intervention administered prior to high-risk surgery is feasible and safe at a tertiary VA hospital. The intervention will consist of individualized exercise training delivered remotely using VA telehealth technology, combined with nutritional support consisting of tailored nutritional advice, protein supplementation, and multivitamin and vitamin D supplements. Based on local surgical volume, local expertise in the Gerofit and telehealth exercise programs in non-surgical populations, and published participation numbers and attrition rates, we anticipate that 24 patients can be enrolled and safely participate in a home-based telehealth exercise program plus nutritional support. Adherence to the intervention will be encouraged by use of automated text messages.

This is a pilot intervention that combines the most promising elements of prehabilitation along with innovations in telehealth delivery to develop a VA patient-centered multimodal prehabilitation program with the following specific aims:

- To determine the feasibility, acceptability, and safety of a short-term (3-4 week) multimodal prehabilitation intervention followed by a 4-6 week period of rehabilitation in a cohort of veterans undergoing high-risk surgery.
- To estimate the effect size of a multimodal prehabilitation program for important postoperative outcomes (improvements in functional capacity and physical function, anxiety/depression, and quality of life).

While aspects of the intervention are novel and the work exploratory, based on available evidence, we expect the Cohen’s effect sizes for functional capacity and quality of life to be approximately 1.6 and 0.4, respectively.

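### Section 8.2.3 schedules the SF-36 at five time points, but Table 1, which it names for timelines, lists three and omits the only assessment between prehabilitation and surgery.

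*Combined protocol and SAP*

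**What the plan says.** Section 8.2.3 puts the two questionnaires on one schedule: "HADS and SF-36 questionnaires at baseline (T1), before surgery (T2), immediately prior to hospital discharge (T3), and 6 and 24 weeks postoperatively", the last two being T4 and T5. It closes with "Details and timelines for each of these assessment instruments are described in Table 1". In that table the HADS row reads T1, T2, T3, T4, T5, and the SF-36 row just above it reads T1, T4, T5.

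Both schedules include the baseline. Section 8.1 lists, for patients who consent, "assessment of handgrip strength (HGS), and the PG-GSA, SF-36 and HADS questionnaires".

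The analysis in Section 13.0 is "Changes in health-related quality of life (SF-36) and anxiety and depression (HADS) before surgery and at the 6-week and 24-week study periods following surgery", with no T-codes. Aim 2 in Section 3.0 is to estimate effect sizes "for important postoperative outcomes (improvements in functional capacity and physical function, anxiety/depression, and quality of life"), and the same section expects a Cohen's effect size of about 0.4 for quality of life.

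**The concern.** One sentence gives the SF-36 and the HADS the same five time points, and the table it points to does not. Because the text names Table 1 as the source for timelines, study staff could reasonably work from the table and omit the SF-36 at T2 and T3. If some follow the text and others the table, data at those visits will be patchy.

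T2 matters most. It is the only assessment between the end of prehabilitation and the operation. Without it, every available SF-36 change includes the effect of major surgery, and the missing value cannot be obtained once a participant has passed that point. The HADS would have a preoperative change and the SF-36 would not, although Aim 2 names both domains.

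**Working it through.** **1. The two SF-36 schedules**

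| Source | SF-36 | HADS |
|---|---|---|
| Section 8.2.3, text | T1, T2, T3, T4, T5 | T1, T2, T3, T4, T5 |
| Section 8.2.3, Table 1 | T1, T4, T5 | T1, T2, T3, T4, T5 |

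The time points in the text but not in the table are T2 and T3.

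**2. Is this an isolated slip or a reading error?** Seven instruments have fixed visits. For 5RSTS, the step test, handgrip strength, anthropometrics and PG-SGA, text and table both give T1 to T4. For the HADS, both give T1 to T5. Six of seven agree, and the SF-36 is the only mismatch. Its table entry is a clean list and the neighbouring HADS entry is complete, so an error in extracting the table is unlikely.

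**3. What T2 represents.** Section 8.2.3 defines the interval: "Messages will be sent daily using the VA Annie App during the prehabilitation period (T1 - T2"). Section 10.0 places T2 on the day of surgery or at an "optional second preop visit immediately prior to surgery if the T2 assessment cannot be performed on the day of surgery". T2 therefore closes prehabilitation and precedes the operation, and no other assessment does.

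**4. Does Section 13.0 settle it?** It turns on what *before surgery* means there.
- If it means T2, as in Section 8.2.3, which attaches that phrase to T2 each time it lists the visits, the planned preoperative SF-36 value is not collected under Table 1.
- If it means the T1 clinic visit, the planned changes are T1 to T4 and T1 to T5, and both schedules supply them.

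The section does not say which, so it cannot decide between the schedules.

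**5. Number of administrations in dispute.** The planned enrolment is 24 (Sections 3.0 and 5.1).
- Section 8.2.3: 5 × 24 = 120
- Table 1: 3 × 24 = 72
- Difference: 120 − 72 = 48, and 48/120 = 40%, made up of 24 at T2 and 24 at T3

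With an assumed 25% loss (n = 18), the counts are 5 × 18 = 90 and 3 × 18 = 54, a difference of 36.

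**6. What a T2 measurement would provide.** The 95% confidence interval for a mean paired change has half-width t(0.975, n − 1)/√n, in units of the SD of change:
- n = 24: 0.42
- n = 20: 0.47
- n = 18: 0.50

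The values n = 20 and n = 18 are assumptions about attrition. If T2 is not collected, there is no estimate of this change at any precision.

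**The case against.** The strongest reply is that no clearly planned analysis is lost. Section 13.0 reserves the comparison before and after prehabilitation, with Cohen's d, for the two physical-function tests. For the SF-36 it asks only for changes and names no T1-to-T2 contrast. Aim 2 speaks of postoperative outcomes, and the three occasions in Section 13.0 fit T1, T4 and T5. On that view Table 1 may be what was intended, and its being named for timelines points the same way.

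Much of this stands. The three-point schedule may be the intended one. The T1-to-T4 and T1-to-T5 changes survive either way. The expected 0.4 is not tied to the T1-to-T2 interval. In a single-arm pilot, a T1-to-T2 change would exclude the operation but would not by itself isolate the program's effect.

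It does not remove the conflict. A pointer to a table is not a rule of precedence when the sentence just before it gives a different schedule. The Section 13.0 sentence covers the HADS as well, which has five time points in both places, so its three occasions are no evidence for a three-point SF-36.

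Two further objections are fair. Half of the 48 administrations are at T3, for which Section 13.0 names no contrast; only the 24 at T2 (24/120 = 20%) bear on the lost preoperative change. The half-widths describe what T2 data would offer and do not measure the size of the error. Finally, Figure 1 was not available for this review. It may show which schedule was meant, but it cannot make the text and Table 1 agree.

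**Conclusion.** The contradiction is real and should be fixed; confidence is high. The SF-36 has five time points in the text and three in Table 1, and the disputed ones are T2 and T3. The 48 disputed administrations (40%) are an upper bound that assumes 24 participants, no withdrawals and uniform use of Table 1. The material consequence is the possible loss of all 24 T2 values, and with them any SF-36 change that excludes surgery.

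Feasibility, acceptability and safety (Aim 1), the physical-function effect sizes, and the SF-36 changes from T1 to 6 and 24 weeks are not affected. Whether a planned preoperative SF-36 analysis becomes impossible depends on the meaning of *before surgery* in Section 13.0, which is itself undefined.

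**What to change.** Make the text and the table agree, and check Figure 1 against the result.

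- If five time points are intended, change the SF-36 row of Table 1 to T1, T2, T3, T4, T5, matching Section 8.2.3 and the HADS row. This is preferable if a preoperative quality-of-life change is wanted.
- If three are intended, separate the SF-36 from the HADS in Section 8.2.3 and state that no T1-to-T2 SF-36 change will be reported.
- In either case, name the reference time point in Section 13.0. Using T1 for both instruments would give T1 to T2 (where collected), T1 to T4 and T1 to T5.

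The edit is one table cell or one sentence, plus one sentence in Section 13.0 and any matching change to Figure 1. Keeping five time points means two more SF-36 questionnaires per participant than Table 1 requires. They fall at contacts that already collect the HADS and may be done in person, by telephone or by videoconference.
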